ARM 1: AM0010 (5 µg/kg) subcutaneous (SQ) dosed on Days 1–5 (with rest on Days 6 and 7) and Days 8–12 SQ (with rest on Days 13 and 14) plus a FOLFOX regimen (a 2-hour infusion of *dl*-LV 400 mg/m² and oxaliplatin 85 mg/m² followed by bolus 5-FU 400 mg/m² and a 46- to 48-hour infusion of 5-FU 2400 mg/m²) initiated on Day 1 of a 14-day cycle for up to 12 cycles or until disease progression by RECIST v.1.1.

While receiving FOLFOX during Cycles 1–12, AM0010 at 5 µg/kg will be administered as 1 of 2 fixed doses, either 0.4 mg for patients weighing ≤80 kg or 0.8 mg for patients weighing >80 kg.

Patients in ARM 1 may continue on maintenance cycles with AM0010 (as shown below). After discontinuation of FOLFOX in the absence of tumor progression (ie, completion of the planned 12 cycles or unacceptable FOLFOX related toxicity), AM0010 at 10 µg/kg will be administered as 1 of 2 fixed doses, either 0.8 mg for patients weighing ≤80 kg or 1.6 mg for patients weighing >80 kg.

ARM 1: AM0010 plus FOLFOX, for up to 12 cycles or until disease progression by RECIST v.1.1.

ARM 1: AM0010 plus FOLFOX

[figure not shown]

ARM 1 in the absence of tumor progression may continue maintenance with AM0010 alone at either 0.4 mg for patients weighing ≤ 80 kg or 0.8 mg for patients weighing > 80 kg after completion of FOLFOX or FOLFOX intolerance

ARM 2: FOLFOX alone, initiated on Day 1 of a 14-day cycle, for up to 12 cycles or until disease progression by RECIST v.1.1.

**Study Design
(continued)**

ARM 2: FOLFOX Alone

[figure not shown]

Crossover of patients from the FOLFOX-only treatment arm into the FOLFOX plus AM0010 treatment arm is not permitted.

Patients randomized to the investigational combination treatment (AM0010 plus FOLFOX) ARM 1, after completion of up to 12 cycles of combination chemotherapy or if experiencing chemotherapy intolerance (as defined as Grade 3 or 4 non-hematologic toxicity that does not resolve to baseline in 28 days with standard of care or hematologic Grade 4 toxicity that does not resolve to baseline in 28 days), may continue to receive maintenance AM0010 if the patient continues to receive clinical benefit (CR, PR, SD).

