2.2 Study Design

This is a randomized, open label, global Phase 3 Study of AM0010 in combination with FOLFOX compared with FOLFOX alone as second-line therapy in patients with advanced metastatic pancreatic cancer that has progressed during or following a first-line gemcitabine-containing regimen.

Approximately 566 patients will be randomized. Two interim analyses are planned. The first interim analysis will be performed when at least 60 randomized patients have had the opportunity to receive 4 months of therapy from the date of Randomization. Based on the first interim analysis, the Data Monitoring Committee (DMC) will review the PK exposure-safety and PK exposure-efficacy on the composite aggregate data for a Go/No-Go decision to enroll the entire Phase 3 study. The enrollment will continue during the analysis. The second interim analysis will occur when approximately 276 deaths (70% of total 393 deaths needed for final analysis) have occurred. Based on the second interim analysis, the DMC will recommend modifying, continuing the trial as planned, or discontinuing the trial.

Patients will be randomized in a 1:1 ratio to AM0010 combined with FOLFOX or FOLFOX alone.

The randomization will be stratified by 2 stratification factors:

- Prior single-agent gemcitabine therapy versus gemcitabine/nab-paclitaxel therapy
- North America versus Europe versus APAC.

Treatment Arms:

[figure not shown]
ARM 1: AM0010 (5 µg/kg) SQ dosed on Days 1–5 (with rest on Days 6 and 7) and Days 8-12 SQ (with rest on Days 13 and 14) plus FOLFOX (*dl*-LV 400 mg/m² and oxaliplatin 85 mg/m² followed by bolus 5-FU 400 mg/m² and a 46- to 48-hour infusion of 5-FU 2400 mg/m²) initiated on Day 1 of a 14-day cycle, for up to 12 cycles or until disease progression by RECIST v.1.1.

While receiving FOLFOX during Cycles 1–12, AM0010 at 5 µg/kg will be administered as 1 of 2 fixed doses, either 0.4 mg for patients weighing ≤80 kg or 0.8 mg for patients weighing >80 kg.

Patients in ARM 1 may continue on maintenance cycles with AM0010 (as shown below). After discontinuation of FOLFOX in the absence of tumor progression (ie, completion of the planned 12 cycles or unacceptable FOLFOX related toxicity), AM0010 at 10 µg/kg will be administered as 1 of 2 fixed doses, either 0.8 mg patients weighing ≤80 kg or 1.6 mg for patients weighing >80 kg.

ARM 1: AM0010 plus FOLFOX, for up to 12 cycles or until disease progression by RECIST v.1.1.

Figure 4: ARM 1: AM0010 + FOLFOX

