5.1 Treatment Administration

5.1.1 AM0010

AM0010 is provided as a sterile, clear solution formulated at a concentration of 2 mg/mL and 4 mg/mL.

The AM0010 drug product is stored at the pharmacy at 2°C to 8°C. Patients will store their AM0010 in their refrigerator (2°C to 8°C).

While receiving FOLFOX during Cycles 1–12, AM0010 5 µg/kg will be administered as 1 of 2 fixed doses, either 0.4 mg for patients weighing ≤80 kg or 0.8 mg for patients weighing >80 kg.

AM0010 will be administered as a fixed dose, bracketed in 2 weight groups. Ongoing PK analysis has shown that the apparent clearance is proportional to weight supporting a weight-based dosing.

The rationale for dosing at a flat rate with a cutoff at 80 kg is based on safety and on the PK/Pharmacodynamic relationship. More specifically, immune activation with AM0010 requires a serum trough of at least 1 ng/mL. This trough level is reached with actual doses of 2.5 µg/kg and higher. The MTD of AM0010 is 20 µg/kg. Following the bracketed fixed dosing regimen, all patients will receive between 5 and 10 µg/kg AM0010. This dose range correlated with a survival benefit in a Phase 1b study with AM0010 + FOLFOX in PDAC patients.

The effects of overdose with AM0010 and an antidote to overdose with AM0010 are unknown. Non-human primates have been exposed to 5-10 times the expected serum concentration in humans without acute adverse reactions.

For any subject experiencing AM0010 overdose, observation for any symptomatic side effects should be instituted and vital signs and biochemical and hematologic parameters should be followed closely

(consistent with the protocol or more frequently, as needed). Appropriate supportive management to mitigate adverse effects should be initiated.

After discontinuation of FOLFOX (ie, completion of the planned 12 cycles or unacceptable FOLFOX-related toxicity), the AM0010 dose at the 10- $\mu\text{g}/\text{kg}$ dose level will be administered as 1 of 2 fixed doses (ie, either 0.8 mg in 0.2 mL for body weight ≤ 80 kg or 1.6 mg in 0.4 mL for body weight > 80 kg), based on the patient's weight during the course of the study.

In 144 patients who received AM0010 monotherapy, the MTD was determined at 20 $\mu\text{g}/\text{kg}$ (Naing et al., 2016). Pharmacodynamic analysis indicates immune activation at 10 $\mu\text{g}/\text{kg}$ in a monotherapy setting.

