5.1.3 Dosing Schedule

Patients will be treated on an outpatient basis with AM0010 plus FOLFOX or FOLFOX alone. Each cycle is 14 days.

ARM 1: AM0010 plus FOLFOX

[figure not shown]
AM0010 dose should be administered on Days 1–5 and Days 8–12 in the morning, ideally with 24 hours (± 2 hours) between doses. Days 6, 7, 13, and 14 will be rest days. FOLFOX dosing should be initiated on Day 1 of each cycle, after AM0010 administration on investigational ARM 1 (Figure 7). ARM 2 consists of FOLFOX administration alone as shown below, initiated on Day 1 of a 14-day cycle (Figure 8).

For patients in the combination therapy (AM0010 + FOLFOX) arm, after the last scheduled chemotherapy cycle in the absence of tumor progression, up to 12 cycles, or chemotherapy intolerance, maintenance dosing of AM0010 may continue 5 days on and 2 days off at 10 $\mu\text{g}/\text{kg}$ SQ qd (see Section 5.1.1).

Crossover of patients from the FOLFOX-only treatment arm into the FOLFOX plus AM0010 treatment arm is not permitted. Supportive care per the institution's normal standard of care, including concomitant medications, can be provided at the Investigator's discretion.

[figure not shown]
The documentation of the investigational product administration will be noted on the CRF page and in the source documentation. The date, dose volume, and time of administration for each dose will be recorded in the patient diary and on the respective CRF page. Details of preparing and administering AM0010 will be provided to the patient and are included in the Pharmacy Manual.

Figure 7: ARM 1: AM0010 + FOLFOX

ARM 1 in the absence of tumor progression may continue maintenance with AM0010 alone at either 0.4 mg for patients weighing ≤ 80 kg or 0.8 mg for patients weighing > 80 kg after completion of FOLFOX or FOLFOX intolerance

Figure 8: ARM 2: FOLFOX Alone

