6.3 ARM 1 Subsequent Cycles AFTER Discontinuation of FOLFOX

6.3.1 ARM 1 (Investigational) Maintenance Cycles after Termination of FOLFOX (Every 28 Days)

In the absence of tumor progression, after completion of up to 12 planned cycles of FOLFOX or discontinuation of FOLFOX due to toxicity, patients assigned to ARM 1 may continue on AM0010 monotherapy at 10 µg/kg (either 0.8 mg for patients weighing ≤80 kg or 1.6 mg for patients weighing >80 kg, administered 5 days on and 2 days off).

Dose reductions in maintenance are the same as in combination at 80% and 60% by altering dose schedule. The 80% dose is administered 4 days on and 3 days off and the 60% dose is administered 3 days on and 4 days off.

The numbering of cycles during maintenance treatment in ARM 1 will follow the convention of “Maintenance Cycles” with Maintenance C1D1 beginning after discontinuation of FOLFOX and start of monotherapy AM0010 as described above. Each Maintenance Cycle will be 28 days/4 weeks in duration.

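### The text with the Arm 1 figures states maintenance AM0010 as 0.4/0.8 mg in three places, half the 0.8/1.6 mg set by the body text and the SAP

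*Protocol*

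**What the plan says.** The protocol gives two maintenance doses for Arm 1 after FOLFOX ends without progression.

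- **Text with the Arm 1 figures** (Synopsis; Section 2.2 with Figure 4; Section 5.1.3 with Figure 7): Arm 1 "may continue maintenance with AM0010 alone at either 0.4 mg for patients weighing" 80 kg or less, and 0.8 mg above 80 kg.
- **Body text:** in the Synopsis, AM0010 at 10 µg/kg "will be administered as 1 of 2 fixed doses, either 0.8 mg for patients weighing" 80 kg or less, with 1.6 mg above 80 kg. Section 2.2 has the same rule ("will be administered as 1 of 2 fixed doses, either 0.8 mg patients weighing"). Section 5.1.1 adds volumes ("either 0.8 mg in 0.2 mL for body weight" of 80 kg or less; 1.6 mg in 0.4 mL above it). Section 6.3.1 gives 0.8 mg or "1.6 mg for patients weighing >80 kg, administered 5 days on and 2 days off".
- **Section 5.1.3 contains both.** Its body text says "maintenance dosing of AM0010 may continue 5 days on and 2 days off at 10" µg/kg and points to Section 5.1.1, while its figure text says 0.4/0.8 mg.

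Section 1.3.2 explains why 10 µg/kg was chosen for maintenance. SAP 6.3 repeats 0.8/1.6 mg, and SAP 10.1.1 describes maintenance as double the earlier dose, 8 or 16 mg per 2 weeks. In Appendix A, the AM0010 treatment row is marked in the maintenance column, but its footnote g states only 5 µg/kg.

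**The concern.** The conflict is twofold in the investigational drug, and it sits where staff look up a dose: the design schema and the Dosing Schedule section. Patients or caregivers give the injections at home, so one wrong dispensing instruction could repeat through a whole 28-day maintenance cycle. The Schedule of Events does not resolve the conflict, because footnote g mentions only the combination dose level.

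At stake are the dose delivered in the maintenance phase and the maintenance exposure summary in SAP 10.1.1, which would then describe a dose that nobody chose. No inferential analysis depends on this point.

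**Working it through.** **Which version is wrong.** Section 5.1.1 gives 0.4/0.8 mg for Cycles 1–12 with FOLFOX, so the figure text repeats the combination dose. Every other statement of the maintenance dose in the body text, the rationale and the SAP gives 10 µg/kg, 0.8/1.6 mg, or twice the combination amount. Nothing in the documents argues for 5 µg/kg in maintenance.

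**Reproducing the SAP's planned amounts.** Five days on and two off is 10 injections per 14 days and 20 per 28-day maintenance cycle.

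| | ≤80 kg, per 14 days | >80 kg, per 14 days | ≤80 kg, per 28 days | >80 kg, per 28 days |
|---|---|---|---|---|
| Body text (0.8/1.6 mg) | 0.8 × 10 = 8 mg | 1.6 × 10 = 16 mg | 16 mg | 32 mg |
| Figure text (0.4/0.8 mg) | 0.4 × 10 = 4 mg | 0.8 × 10 = 8 mg | 8 mg | 16 mg |

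The body text reproduces the 8 and 16 mg of SAP 10.1.1 exactly. The figure text gives half in both weight groups.

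**Per kilogram.** Dose in mg × 1000 / weight:

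- 60 kg: 0.8 mg gives 13.33 µg/kg; 0.4 mg gives 6.67.
- 80 kg: 0.8 mg gives 10.0; 0.4 mg gives 5.0.
- 100 kg: 1.6 mg gives 16.0; 0.8 mg gives 8.0.

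Over 40–160 kg, the weight range of the protocol's Table 9, the body text delivers 10–20 µg/kg and the figure text 5–10 µg/kg.

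**Effect on relative dose intensity.** SAP 10.1.1 divides cumulative dose by duration, then by the planned dose. For pegilodecakin, duration is last dose minus first dose plus 1, so the final rest days drop out. Applying the same formula within maintenance, against 8 mg per 2 weeks (≤80 kg):

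- *One 28-day cycle* (20 injections, last on day 26, duration 26 days). Correct dose: 16/26 × 14 = 8.62 mg per 2 weeks; 8.62/8 = 107.7%. Figure-text dose: 8/26 × 14 = 4.31; 4.31/8 = 53.8%.
- *Twelve weeks* (60 injections, duration 82 days). Correct dose: 48/82 × 14 = 8.20; 102.4%. Figure-text dose: 24/82 × 14 = 4.10; 51.2%.

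The ratio is always one half, and the two values approach 100% and 50% with longer exposure. The group above 80 kg gives the same percentages.

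**Would the summary reveal the error?** By the same formula, the protocol's reduced schedules at the correct 0.8 mg give, after one cycle:

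- 4 on/3 off: 16 injections, 12.8 mg over 25 days; 12.8/25 × 14 / 8 = 89.6%.
- 3 on/4 off: 12 injections, 9.6 mg over 24 days; 9.6/24 × 14 / 8 = 70.0%.

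A correctly dosed patient on 3 on/4 off who misses 3 of the 12 injections (neither the first nor the last) receives 9 × 0.8 = 7.2 mg; 7.2/24 × 14 / 8 = 52.5%. That is below the 53.8% of an uninterrupted patient on the wrong dose, so a low value does not separate the two.

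**What would separate them.** Section 5.1.3 says "The date, dose volume, and time of administration for each dose will be recorded in the patient diary" and the CRF. Section 5.1.1 describes the product as "formulated at a concentration of 2 mg/mL and 4 mg/mL". A recorded 0.2 mL is 0.2 × 2 = 0.4 mg at one strength and 0.2 × 4 = 0.8 mg at the other, so the dispensed strength is needed as well as the volume.

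**The case against.** The strongest reply is that sites would rarely be misled. The administration section (5.1.1) and the maintenance procedures (6.3.1) both give 0.8/1.6 mg, Section 5.1.3 directs the reader to 5.1.1, and preparation details are in the Pharmacy Manual, which is not among the documents. This stands as a limit on likelihood. It does not remove a wrong dose stated three times in current text.

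Four stronger readings are tempting and not supported:

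- *Patients were underdosed.* The documents show a contradiction, not what was dispensed, and give no basis for a count.
- *Misdosed patients would stand out at 50% relative dose intensity.* The SAP formula gives somewhat more than 50% over finite exposure, and missed injections, toxicity holds or delays can produce similar values.
- *The volumes in 5.1.1 prove which dose is right.* They imply 0.8/0.2 = 4 mg/mL, a supplied strength, but 0.4 mg in 0.2 mL implies 2 mg/mL, also supplied. The conclusion rests on the body text, the rationale and the SAP, which suffice.
- *The lower dose would be inactive.* Section 1.3.2 says the trough needed for immune activation is reached from 2.5 µg/kg, and the figure text stays above that over 40–160 kg. The point is departure from the chosen dose.

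It is also fair to say that only a descriptive summary is touched, since the SAP is consistent on the mg amounts.

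**Conclusion.** The point holds as an internal contradiction in a dose instruction, and the figure text is the wrong side of it. Followed literally, it halves maintenance AM0010 in both weight groups and halves relative dose intensity compared with a correctly dosed patient on the same schedule (about 54% against 108% after one cycle). These percentages assume uninterrupted 5 on/2 off dosing and the SAP duration formula applied within the maintenance period; the factor of one half in mg does not depend on that formula. The number of patients affected, if any, cannot be derived. The error should be fixed because it concerns the investigational drug and is cheap to remove.

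**What to change.** In the Synopsis, Section 2.2 and Section 5.1.3, change the maintenance dose in the text with the Arm 1 figure to 0.8 mg for patients weighing ≤80 kg or 1.6 mg for patients weighing >80 kg. In Appendix A, have footnote g refer also to the 10 µg/kg maintenance dose in Section 5.1.1. Leave Sections 5.1.1 and 6.3.1 and SAP 6.3 and 10.1.1 as they are.

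Because 5.1.1 and 6.3.1 already state the correct dose, this can go to sites promptly as a clarification and be carried into the next amendment. Section 12.2 lists administrative letters among the communications to the IRB/IEC; Section 11.2 requires review before revised procedures are used. If any patient has already entered maintenance, check dispensed strength against recorded volume rather than relying on relative dose intensity.

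The cost is three sentences, one footnote and a notice to about 150 sites. The SAP, visits, sample size and analyses do not change.

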5.2 Dose Interruption, Reduction, and Dose Schedule Modifications

If a non-hematologic AE is attributed to only 1 drug (ie, AM0010, oxaliplatin, or 5-FU), the Investigator should determine if the drug will be continued based on the Investigator's assessment of risk-benefit per the guidelines outlined below. For example, neuropathy, is clearly related to oxaliplatin; therefore, 5-FU/LV as well as AM0010 would not be responsible for this AE.

Hematologic Toxicity Dose Schedule Adjustment Requirements (graded according to the National Cancer Institute Common Terminology Criteria for Adverse Events (NCI CTCAE) v4.03, Appendix G; see also Table 10):

- Thrombocytopenia Grades 3-4 with platelet count $<50,000/\text{mm}^3$: delay treatment with AM0010 and FOLFOX until platelet count returns to $\geq 100,000/\text{mm}^3$. Re-introduction of AM0010 should be administered at 80% and FOLFOX at dose level -1. If on a subsequent cycle these toxicities recur, AM0010 is reintroduced at 60% (-2 dose level) and FOLFOX at dose level -2 after the first recurrence. This will be accomplished by altering the dose schedule from 5 days on and 2 days off to 4 days on and 3 days off (80%), and 3 days on 4 days off (60%), respectively.
- Anemia Grades 3-4 with Hgb <8 g/dL: delay treatment with AM0010 and FOLFOX until Hgb returns to ≥ 10 g/dL. Re-introduction of AM0010 should occur at 80% and FOLFOX at dose level -1. If on a subsequent cycle these toxicities recur, AM0010 is reintroduced at 60% and FOLFOX at dose level -2 after the first recurrence.

Table 10: Hematologic Toxicity Dose Schedule Adjustment (Thrombocytopenia and Anemia Only)

| Occurrence of Hematologic TrAE* | FOLFOX Reintroduction | AM0010 Re-Introduction Dosing | Day 1 (FOLFOX Start) | Day 2 (FOLFOX End) | Day 3 | Day 4 | Day 5 | Day 6 | Day 7 |
|---------------------------------|-----------------------|-------------------------------|----------------------|--------------------|-------|-------|-------|-------|-------|
| – | Full dose | 100% | X | X | X | X | X | Rest | Rest |
| 1 st | –1 | 80% | X | X | X | X | Rest | Rest | Rest |
| 2 nd | –2 | 60% | X | X | X | Rest | Rest | Rest | Rest |

TrAE = Treatment-related Adverse Event; X = dosing

- Neutropenia and neutropenic fever Grades 3–4 with ANC $<1,000/\text{mm}^3$: delay treatment with FOLFOX until ANC returns to $>1,000/\text{mm}^3$. Re-introduction of FOLFOX should occur at dose level –1. If on a subsequent cycle these toxicities recur, FOLFOX is reduced to dose level –2 after the first recurrence. AM0010 dosing will continue without interruption.

Non-Hematologic Toxicity Dose Schedule Adjustment Requirements (graded according to the NCI CTCAE v4.03, [Appendix G](#)):

- \geq Grade 3 fatigue, elevations in AST, ALT, alkaline phosphatase, or bilirubin require dose interruption and delay in subsequent therapy until recovered to \leq Grade 1 or pre-therapy baseline. Re-introduction of all agents at the previous dose level.
- \geq Grade 3 GI AEs such as diarrhea, nausea, vomiting, abdominal pain, and bloating require a delay in subsequent therapy until recovered to \leq Grade 1 or pre-therapy baseline. Re-introduction: Reduce offending agent by 1 dose level. Keep other agents unchanged.
- Other non-hematologic toxicities with an impact on organ function of \geq Grade 3 require dose reduction. Hold treatment for the offending agent (or all agents, see [Table 11](#)), delay in subsequent therapy until recovered to \leq Grade 1 or pre-therapy baseline. Re-introduction: Reduce offending agent by 1 dose level. Keep other agents unchanged.
If AM0010 is suspected to be one of the offending agents, reintroduction will be at the original dose after the first occurrence. If on a subsequent cycle these toxicities recur, the AM0010 treatment schedule will be decreased to 80%. Upon second recurrence of Grade 3 or 4 AE, the AM0010 dose will be decreased to 60%. This will be accomplished by altering the dose schedule from 5 days on and 2 days off to 4 days on and 3 days off (80%), and 3 days on 4 days off (60%), respectively. See below.
- It is common for oxaliplatin to cause Grade 3 or 4 neuropathy by 4 months of therapy. On both treatment arms following the dose modification in [Table 11](#) for neuropathy, if oxaliplatin needs to be discontinued, continue therapy with 5-FU/LV.

Table 11: Dose Interruption, Reduction, and Dose Schedule Modifications

| Adverse Event | Occurrence | Oxaliplatin | 5-Fluorouracil | AM0010 |
|---|-----------------|--|---|---|
| Hematological AEs | | | | |
| Grades 3-4 Anemia or Grades 3-4 Thrombocytopenia | 1 st | Hold until G1 or baseline Reintroduce at dose level –1 | Hold until G1 or baseline Reintroduce at dose level –1 | Hold until G1 or baseline Reintroduce to Dose Level –1 |
| | 2 nd | Hold until G1 or baseline Reintroduce at dose level –2 | Hold until G1 or baseline Reintroduce at dose level –2 | Hold until G1 or baseline reintroduce to Dose Level –2 |
| | 3 rd | Hold until G1 or baseline No change in dose | Hold until G1 or baseline No change in dose | Hold until G1 or baseline No change in dose |
| Grades 3–4 neutropenia or Grades 3–4 leukopenia or Grades 3–4 neutropenic fever | 1 st | Hold until G1 or baseline Reintroduce at dose level –1 | Hold until G1 or baseline Reintroduce at dose level –1 | Continue dosing; no change in dose schedule |
| | 2 nd | Hold until G1 or baseline Reintroduce at dose level –2 | Hold until G1 or baseline Reintroduce at dose level –2 | |
| Hemolytic uremic syndrome (HUS) ² | 1 st | Discontinue | Hold until G1 or baseline No change in dose | Hold until G1 or baseline No change in dose |
| Non-hematological AEs | | | | |
| Grade 3 Diarrhea | | Hold until G1 or baseline No change in dose level | Hold until G1 or baseline Reintroduce at dose level –1 | Continue dosing; no change in dose schedule |
| Grade 4 Diarrhea | | Hold until G1 or baseline Reintroduce at dose level –1 | Hold until G1 or baseline Reintroduce at dose level –1 | |
| Cough ≥Grade 3 Dyspnea ≥Grade 3 Hypoxia ≥Grade 3 Pneumonitis ≥Grade 3 | | Hold oxaliplatin until interstitial lung disease is ruled out. If interstitial lung disease, discontinue oxaliplatin. | Hold until G1 or baseline No change in dose | Hold until G1 or baseline No change in dose schedule |
| Grade 3 Fatigue | | Hold until G1 or baseline No change in dose level | Hold until G1 or baseline No change in dose level | Hold until G1 or baseline No change in dose schedule |

Table 11: Dose Interruption, Reduction, and Dose Schedule Modifications

| Adverse Event | Occurrence | Oxaliplatin | 5-Fluorouracil | AM0010 |
|--|------------|--|-------------------|---|
| Non-hematological AEs | | | | |
| Other G3/G4 non-hematological AEs ^{3,4} | | Hold until G1 or baseline Reduce offending agent by 1 dose level ¹ | | No change in dose schedule |
| Hypomagnesemia | | Hold until G1 or baseline No change in dose level | | |
| Neurological AEs | | | | |
| Persistent ⁵ Grade 2 Paresthesias/ Dysesthesias ⁶ | | Reduce dose to level –1 | No change in dose | Continue dosing; no change in dose schedule |
| Grade 3 Paresthesias/ dysesthesias ⁶ Dysesthesias ⁶ | | Hold until G1 or baseline Discontinue, if persistent ⁵ | | |
| Grade 4 Paresthesias/ dysesthesias ⁶ Dysesthesias ⁶ | | Discontinue | | |
| Grade 2 = moderate (also recommended is administration of benzodiazepine and patient education. Management of patient if ≥ Grade 2 laryngeal dysesthesias occurs while treatment is being administered.) Grade 3 = severe | | Stop oxaliplatin infusion. Administer benzodiazepine and give patient reassurance. At the discretion of the Investigator, the infusion can be restarted at 1/3 the original rate of infusion. Continue 5-FU | | Continue dosing; no change in dose schedule |

¹ If an AE is believed likely to be due to only 1 of the drugs, it is permissible to decrease dose of that drug only.² Recommended evaluation of suspected HUS: Evaluation should include complete blood count (CBC) differential, platelets, PT, PTT, fibrinogen, FDP, Anti thrombin III, Von Willebrand factor, anti-nuclear antibody, rheumatoid factor, Compliment Cascade C3, C4, and CH50, anti-platelet antibodies, platelet-associated IgG, and circulating immune complexes. Renal evaluation should include creatinine, BUN, and urinalysis. Other laboratory and hematologic evaluations as appropriate should also be obtained, including peripheral blood smear and free hemoglobin.³ Exceptions: fatigue, anorexia, nausea/vomiting if can be controlled by antiemetics, and viral infections.⁴ Dose modifications for other non-hematologic adverse events at the start of subsequent courses of therapy, and at time of retreatment are also based on NCI CTCAE v4.03 criteria.⁵ Not resolved by the beginning of the next cycle.⁶ May be cold-induced.

